8.2.2 Malignancies

8.2.2.1 Cutaneous squamous cell carcinoma (cuSCC)

Cases of cuSCC (which include those classified as KA or mixed KA subtype) have been observed in subjects treated with dabrafenib and the combination of dabrafenib and trametinib [GlaxoSmithKline Document Number [CM2010/00010/05](#)].

In a Phase III study, 10% of patients receiving dabrafenib monotherapy developed cuSCC, with a median time to onset of the first occurrence of approximately 8 weeks. In patients who received dabrafenib in combination with trametinib, 3% of patients developed cuSCC with median time to onset of the first occurrence of 32 weeks.

CuSCC/KA should be surgically removed according to institutional practices. Dose modification or interruption of study treatment is not required for cuSCC or KA, however cuSCC should be reported as an SAE. Tumor tissue should also be submitted for further analyses as described in the SPM.

Subjects should be instructed to immediately inform their physician if new lesions develop. Skin examination should be performed prior to initiation of dabrafenib and during treatment with dabrafenib, every 2 months throughout therapy. Monitoring should continue every 2 to 3 months for 6 months following discontinuation of dabrafenib or until initiation of another anti-neoplastic therapy.

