Protocol waivers or exemptions are not allowed with the exception of immediate safety concerns. Therefore, adherence to the study design requirements, including those specified in the Time and Events Table (Section 7.1) is essential and required for study conduct. Supplementary study conduct information not mandated to be present in this protocol is provided in the accompanying study procedures manual (SPM). The SPM will provide site personnel with administrative and detailed technical information that does not impact subject safety.

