 10. **BRIEF PHYSICAL EXAM:** A brief physical exam will be performed on Day 1 (if more than 72 hrs since the complete physical exam was performed for Screening) and every 4 weeks while on study treatment.
 11. **HEIGHT:** Height will be measured as part of complete physical exam performed at Screening only.
 12. **FULL DERMATOLOGICAL EXAM:** A full dermatological exam will be performed at Screening (or within 35 days prior to the first dose) only. A biopsy in and/or around a new skin lesion(s) or a lesion(s) that changes during the study is required if clinically indicated (refer to Section 7.4.2).
 13. **BRIEF DERMATOLOGICAL EXAM:** A brief dermatological exam will be performed every 4 weeks thereafter unless otherwise required to be performed more frequently. A brief dermatological exam should be performed every 4 weeks (± 7 days) for the first 6 months after discontinuation of study treatments. A biopsy in and/or around a new skin lesion(s) or a lesion(s) that changes during the study is required if clinically indicated (refer to Section 7.4.2).
 14. **OPHTHALMIC EXAM:** Ophthalmic exams will be performed at Screening (or within 35 days prior to the first dose), Week 4, and as clinically indicated thereafter.
 15. **VITAL SIGNS:** *Vital signs* include systolic/diastolic BP, temperature, pulse rate and respiratory rate. Vital signs should be measured in a semi-supine position after a 5 minute rest. *Blood pressure:* Three readings of BP and pulse rate should be taken. The first reading should be rejected and the second and third readings averaged to give the measurement to be recorded in the eCRF. If persistent hypertension (see Section 8.1.1.3.1) is noted in 3 consecutive visits, clinic visits to monitor the increased BP should be scheduled independently from the per-protocol visits. Ideally, subsequent BP assessments should be performed within 7 days of initial finding.
 16. **ECG:** A single 12-lead ECG should be performed after vital signs and before blood draws if assessments are planned at the same nominal time point. If clinically significant abnormality(ies) are seen, confirm with 2 additional ECGs taken at least 5 minutes apart. See Section 7.4.6 and SPM for additional information on ECG collection.
 17. **ECHO:** ECHOs will be performed at Screening (or within 35 days prior to the first dose), Week 4, Week 12, and then every 12 weeks thereafter. See Section 7.4.7 and SPM for additional information on ECHO collection.
- [REDACTED]

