45. **PK Sampling - Week 8, Week 12, and Follow-up Visit:** A single 2 mL blood sample for PK analysis of trametinib, dabrafenib and its metabolites (hydroxy-dabrafenib and desmethyl-dabrafenib) will be collected at Week 8 (pre-dose), Week 12 (pre-dose), and at the Follow-up Visit. Subjects with morning clinic visits are to be instructed to withhold their morning doses of study treatment and PK samples will be collected prior to dabrafenib administration. Subjects with afternoon clinic visits are to be instructed to take their morning doses as usual and PK samples will be collected 4 to 8 hrs following dabrafenib administration. **Samples at the Follow-up Visit are no longer requested for collection as of Protocol Amendment 11.**

[REDACTED]

- 
54. **STUDY TREATMENT:** Subjects must receive their supply of study treatments within 3 days of enrollment.
55. **FOLLOW-UP VISIT:** The Follow-up Visit should take place within 28 days (+7 days) of the last dose of study treatments. If the subject is unable to return to clinic, site staff is encouraged to call subject for assessment of AEs.
56. **FOLLOW-UP VISIT:** All safety and laboratory assessments should be performed unless the assessments were performed within 4 weeks prior to the Follow-up Visit.
57. **FOLLOW-UP VISIT:** If the last cardiac assessment was >12 weeks prior to the Follow-up Visit, an ECHO should be performed.
58. **EXTENDED FOLLOW-UP:** The following evaluations will be performed for all patients in all cohorts.
- a) Dermatologic exam. Exams will be performed every 4 weeks (+/-7 days) for the first 6 months. The skin will be carefully examined and pictures and biopsy will be taken of any new or changed skin lesions.
 - b) If study treatments are permanently discontinued prior to the subject having confirmed disease progression, the subject will continue to have disease assessments every 12 weeks (+/-14 days) until disease progression or initiation of new anti-cancer treatment, or death, whichever comes first.
 - c) Subjects will be followed every 12 weeks (+/-14 days) for survival until the subject dies or withdraws consent or is lost to follow up, or up to a time period as defined in Section 16.3. Survival follow up may be performed via clinic visit, a telephone contact, an email or by mail. The initiation of any new anti-cancer treatment(s) and date of last contact should also be documented.

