7.4.2 Dermatological Examinations

Dermatological examinations will be performed by an investigator or the subject may be referred to a dermatologist, at the discretion of the investigator. A complete or full body dermatological examination will be performed at the time points indicated in the Time and Event Table (Section 7.1) to identify any abnormal skin lesions. All abnormal findings (i.e.,

suspicious for proliferative skin lesions) will be identified and photographed during the Screening examination. Brief dermatological examinations should be performed every 4 weeks or more frequently if clinically indicated while on study treatment and every 4 weeks (± 7 days) for the first 6 months following treatment discontinuation. Wherever possible, the same individual should perform all of the examinations. Follow-up skin examinations by a referral dermatologist should be conducted if clinically indicated.

Biopsy in or around new skin lesions or lesions that change during the study is required if clinically indicated.

[REDACTED] A summary of the results should be submitted to the sponsor.

Skin photography of new lesions or lesions that change during the study must be obtained and forwarded to the sponsor. Refer to the SPM for details regarding skin lesion documentation by photography.

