8.2.2.2 New Primary Melanoma

New primary melanomas have been reported in subjects treated with dabrafenib. These were identified primarily within the first 5 months of therapy and did not require treatment modification other than excision; however, a new primary melanoma should be reported as an SAE. Monitoring for skin lesions should continue every 2 to 3 months for 6 months following discontinuation of dabrafenib or until initiation of another anti-neoplastic therapy.

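### Sections 8.2.2.1 and 8.2.2.2 set skin-examination intervals two to three times longer than the binding 4-weekly schedule, with a stop at new therapy that the schedule does not contain

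*Protocol*

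**What the plan says.** Section 8.2.2.1 of the protocol, on cutaneous squamous cell carcinoma, sets an on-treatment interval: "Skin examination should be performed prior to initiation of dabrafenib and during treatment with dabrafenib, every 2 months throughout therapy". For the period afterwards it says: "Monitoring should continue every 2 to 3 months for 6 months following discontinuation of dabrafenib or until initiation of another anti-neoplastic therapy". Section 8.2.2.2, on new primary melanoma, gives no on-treatment interval but has the same post-treatment one: "Monitoring for skin lesions should continue every 2 to 3 months for 6 months following discontinuation of dabrafenib". It ends with the same stop at new anti-neoplastic therapy.

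The schedule says otherwise. Footnote 13 of the Time and Event Table reads: "A brief dermatological exam will be performed every 4 weeks thereafter unless otherwise required to be performed more frequently". It then asks for the same 4-weekly examination for 6 months after treatment. Footnote 58a, for extended follow-up, reads: "Exams will be performed every 4 weeks (+/-7 days) for the first 6 months". Footnote 58 introduces its list with: "The following evaluations will be performed for all patients in all cohorts". Section 7.4.2 agrees: "Brief dermatological examinations should be performed every 4 weeks or more frequently if clinically indicated while on study treatment and every 4 weeks", the second interval being for the 6 months after discontinuation. Section 1.4 gives 4-weekly examinations for 6 months after treatment, and Section 16.3 gives monthly examinations for all subjects who stop.

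Section 4 settles which text governs: "adherence to the study design requirements, including those specified in the Time and Events Table (Section 7.1) is essential and required for study conduct".

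**The concern.** Section 8.2.2 is where a site looks when it has to manage skin cancer, a known risk of dabrafenib. Section 8.2.2.1 itself cites cutaneous squamous cell carcinoma in 3% of patients on the combination, with median onset at 32 weeks. It tells the site how often to look, and that frequency would breach the schedule. A site could follow the section in good faith and deviate from the protocol.

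The two periods differ in what is at stake. On treatment, the brief physical examination every 4 weeks includes the skin (Section 7.4.1), so the skin is still seen. After treatment, the last scheduled physical examination that covers the skin is at the Follow-up Visit, within 28 (+7) days of the last dose. From then on the dermatological examination is the only scheduled check of the skin as a whole. The head and neck examination in footnote 58d is 12-weekly and, under footnote 23, need include only the oral mucosa and lymph nodes. Under 8.2.2, subjects who start another anti-neoplastic therapy could lose even the reduced schedule.

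**Working it through.** The plan states no figure to reproduce. The check sets the texts side by side and converts the intervals.

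| Place in protocol | On treatment | 6 months after | Stop at new therapy for skin examinations |
|---|---|---|---|
| 7.1, footnote 13 | 4 weeks | 4 weeks ±7 days | none |
| 7.1, footnote 58a | not covered | 4 weeks ±7 days | none |
| 7.4.2 | 4 weeks or more often | 4 weeks ±7 days | none |
| 16.3 | not covered | monthly ±7 days | none |
| 1.4 | no interval given | 4 weeks ±7 days | mentioned once, in a sentence that refers to 7.1 for the schedule |
| 8.2.2.1 | 2 months | 2 to 3 months | yes |
| 8.2.2.2 | no interval given | 2 to 3 months | yes |

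**Intervals.** The SAP (Section 2.1.1) takes a month as 30.4375 days.
- 2 months: 2 × 30.4375 = 60.9 days, or 8.7 weeks; 8.7/4 = 2.2 times the required interval.
- 3 months: 3 × 30.4375 = 91.3 days, or 13.0 weeks; 13.0/4 = 3.3 times.
- Excess over 28 days: 60.9 − 28 = 33 days, to 91.3 − 28 = 63 days.

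**Can visit windows reconcile them?** The longest gap the table allows is 28 + 3 + 3 = 34 days on treatment (±3 days) and 28 + 7 + 7 = 42 days afterwards (±7 days). The monthly wording in 16.3 allows 30.4 + 7 + 7 = 44.4 days. All are below 60.9 days, so they cannot.

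**Number of examinations.**
- After treatment: 6 × 30.4375/7 = 26.1 weeks; 26.1/4 = 6.5, so 6 examinations. Under 8.2.2 there are 6/2 = 3 or 6/3 = 2.
- On treatment, per year: 52/4 = 13, against 12/2 = 6.

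**Can 8.2.2 be a permitted exception?** No. Footnote 13 and Section 7.4.2 allow departures only towards more frequent examination.

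**Stop at new therapy.** Where the table wants such a stop it writes one: footnote 24 has it for non-cutaneous monitoring. Footnotes 13 and 58a have none for the skin.

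**Reach.** At 06-Apr-2020, 55 of 206 subjects were on treatment (55/206 = 26.7%). On-treatment numbers were 62 at 18-Nov-2019 (Amendment 10) and 55 at 06-Apr-2020. Enrollment was closed and retreatment is barred (Section 16.2), so 62 − 55 = 7 subjects stopped in those 140 days. The number within 6 months of their last dose is not given and was probably small.

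**Reporting after day 30 (for the optional clarification only).** Six months is 182.6 days, so surveillance runs 182.6 − 30 = 152.6 days past the 30-day collection period in Section 11.7 (152.6/182.6 = 84%). Of the nominal post-treatment skin examinations at days 28, 56, 84, 112, 140 and 168, 5 of 6 fall after day 30.

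**The case against.** The strongest reply is that this is an editorial slip. The 4-weekly or monthly rule stands in five other places, the table governs, and Section 8.2 describes its content as brief guidance on dose modification and interruption. A site examining every 4 weeks also satisfies a 2-monthly instruction, so harm needs a site to prefer a toxicity paragraph to the schedule. Much of this stands: the conflict runs one way, and a careful site will resolve it correctly. But the 8.2.2 sentences are operative instructions on examination frequency, not background, and a reader of that section alone is misdirected.

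It can also be said that Section 1.4 carries the stop at new therapy. That sentence defers to Section 7.1, and the same paragraph then gives 4-weekly examinations for 6 months with no stop. It does not support 8.2.2, and it needs no correction of its own.

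Timing is a fair point. Enrollment ended on 29-Jun-2018 and completion is set at about 3 years of minimum follow-up, so roughly a year remained at Amendment 11. Subjects who move to commercial supply or a rollover study may never enter post-treatment follow-up here.

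A reader might go further and infer that the protocol is silent on whether late malignancies judged unrelated are reported as SAEs, so that safety data are being lost. The documents do not support that. Section 11.7 states a rule: all SAEs to day 30, and after that those assessed as related to study participation, study treatment or concomitant medication, up to any follow-up contact. Sections 7.4.9, 8.2.2 and 11.2(h) call new malignancies SAEs without a time or causality limit. They can be read as saying what is serious, not how long to collect it; death and hospitalization in 11.2 carry no such limit either. Reporting regardless of causality to 6 months would be a policy choice. What remains is that a site could read these sections either way.

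**Conclusion.** The interval contradiction holds. Section 8.2.2.1 conflicts with the binding schedule on and after treatment, Section 8.2.2.2 after treatment only, and both add a stop for skin monitoring that the schedule lacks. The size is 2 to 3 examinations instead of 6 in the 6 months after treatment, with a nominal gap 33 to 63 days longer. On treatment it is about 6 instead of 13 dermatological examinations a year, but no detection delay is claimed there, because the brief physical examination still covers the skin every 4 weeks.

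These are nominal counts for a site that follows 8.2.2 instead of the table. The documents do not show that any site did, and they give no post-treatment malignancy rate, so they cannot be turned into missed or delayed cancers. The response-rate analysis is unaffected. So are the SAP analyses: SAP 2.1 and 2.1.1 already include data to death or withdrawal and assign adverse events to a post-therapy period. The reporting question under Section 11.7 is a possible clarification, not an error.

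**What to change.** In Section 8.2.2.1, replace the intervals with every 4 weeks on treatment and every 4 weeks (±7 days) for 6 months afterwards. In Section 8.2.2.2, use the same post-treatment interval. Alternatively, replace both with a reference to Section 7.1. In both sections, delete the stop at new anti-neoplastic therapy for skin examinations.

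The cost is a protocol amendment with IRB/IEC/REB approval. No visits or procedures are added, because Section 4 already schedules extended follow-up visits every 4 weeks for the first 6 months. The change applies prospectively, to subjects on treatment or within 6 months of their last dose.

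Optionally, Section 11.7 could state whether the malignancies listed in 11.2(h) are reported as SAEs regardless of causality during the 6-month surveillance, and whether that ends at new anti-cancer therapy, as non-cutaneous monitoring does. If reporting is widened, the count would mix two collection rules, since 206 − 55 = 151 subjects were already off treatment at 06-Apr-2020 and most were followed under the present rule. Events after day 30 should then be shown separately, using the post-therapy period that SAP 2.1.1 defines.

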8.2.2.2 New Primary Melanoma

New primary melanomas have been reported in subjects treated with dabrafenib. These were identified primarily within the first 5 months of therapy and did not require treatment modification other than excision; however, a new primary melanoma should be reported as an SAE. Monitoring for skin lesions should continue every 2 to 3 months for 6 months following discontinuation of dabrafenib or until initiation of another anti-neoplastic therapy.

8.2.2.3 Non-Cutaneous Malignancies

In vitro experiments have demonstrated paradoxical activation of MAP-kinase signaling in BRAF wild-type cells with RAS mutations when exposed to BRAF inhibitors, which may lead to increased risk of non-cutaneous malignancies in subjects treated with dabrafenib. Cases of RAS-driven malignancies have been seen with BRAF inhibitors.

Subjects should be monitored as clinically appropriate. New non-cutaneous malignancies should be reported as a SAE. Consider the benefits and risks before continuing treatment with dabrafenib in subjects with a non-cutaneous malignancy that has a RAS mutation.

A biopsy of the new malignancy should be taken, where possible, and submitted **locally** for further analyses with the results provided to the sponsor.

Monitoring for non-cutaneous secondary/recurrent malignancies should continue for up to 6 months following discontinuation of dabrafenib or until initiation of another anti-neoplastic therapy.

8.2.3 Pyrexia

Pyrexia, defined as a body temperature $\geq 38.5^{\circ}\text{C}$ (101.3°F), has been observed in subjects receiving dabrafenib monotherapy, and is increased in incidence and severity in subjects receiving dabrafenib in combination with trametinib. In a minority of cases, pyrexia was accompanied by symptoms such as severe chills/rigors, dehydration, hypotension, dizziness or weakness and required hospitalization.

Subjects should be instructed on the importance of immediately reporting febrile episodes. In the event of a fever, the subject should be instructed to take anti-pyretics (i.e., ibuprofen or acetaminophen/paracetamol) as appropriate to control fever. The use of oral corticosteroids should be considered in those instances in which anti-pyretics are insufficient. In subjects experiencing and after pyrexia associated with rigors, severe chills, dehydration, hypotension, serum creatinine and other evidence of renal function should be monitored carefully.

Guidelines regarding management and dose reduction for pyrexia considered to be related to dabrafenib are provided in Table 21.

Table 21 Management and Dose Modification Guidelines for Pyrexia

Occurrence	Action and Dose Modification
Any²	
 1. Clinical evaluation for infection and hypersensitivity³ 2. Laboratory work-up³ 3. Hydration as required⁴
First Event²:	
 1. Administer anti-pyretic treatment if clinically indicated and initiate prophylactic treatment if associated with rigors, renal failure, dehydration or hypotension⁵ 2. Interrupt treatment with dabrafenib; continue treatment with trametinib. 3. Once pyrexia resolves to baseline, restart treatment with dabrafenib at the same dose level; continue treatment with trametinib at current dose level. 4. If fever is associated with dehydration, hypotension, or renal insufficiency, reduce dabrafenib by one dose level; continue treatment with trametinib at current dose level⁷.
Second Event	
 1. Follows same guidelines as for First Event (see above), and 2. Within 3 days of onset 
 • Optimize anti-pyretic therapy • Consider oral corticosteroids (i.e., prednisone 10 mg) for at least 5 days or as clinically indicated⁶
Subsequent Events:	
 1. Interrupt treatment with dabrafenib; continue treatment with trametinib. 2. Once pyrexia resolves to baseline, restart treatment with dabrafenib at dose reduced by one dose level; continue treatment with trametinib at current dose level.⁶ 3. Within 3 days of onset: 
 • Optimize oral corticosteroid dose as clinically indicated for recalcitrant pyrexia.⁷ • If corticosteroids have been tapered and pyrexia recurs, restart steroids. • If corticosteroids cannot be tapered, consult Medical Lead.

Abbreviations: BUN, blood urea nitrogen; CRP, C-reactive protein

1. Pyrexia is defined as a body temperature equal to or above 38.5°C (101.3°F)
2. For subjects experiencing pyrexia complicated by rigors, severe chills, etc., a clinical evaluation and laboratory work-up is mandatory for each event; non-steroidal anti-pyretic treatments should be started immediately at the first occurrence and prophylactic non-steroidal anti-pyretic treatment is recommended when restarting after an interruption.

3. Thorough clinical examination for signs and symptoms of infection or hypersensitivity is required; laboratory work- up should include full-blood-count, electrolytes, creatinine, BUN, CRP, liver function tests, blood culture, and urine culture.
4. Oral hydration should be encouraged in subjects without evidence of dehydration. Intravenous (IV) hydration is recommended in subjects experiencing pyrexia complicated by dehydration/hypotension.
5. Non-steroidal anti-pyretic treatment may include acetaminophen (paracetamol), ibuprofen, or other suitable anti-pyretic medication according to institutional standards. Prophylactic non-steroidal anti-pyretic treatment may be discontinued after 3 days in the absence of pyrexia
NOTE: For subjects with MM, alternative anti-pyretic treatment (i.e., acetaminophen [paracetamol] or other suitable anti-pyretic medication should be taken as NSAIDs are prohibited (see Section 10.2)
6. Dabrafenib should be reduced by one dose level at discretion of the investigator if pyrexia is accompanied by severe recurring rigors which cannot be managed by best supportive care, including increasing doses of oral steroids. Re-escalation of dabrafenib is allowed if no episode of pyrexia is observed in the 4 weeks subsequent to dose reduction.
7. In subjects experiencing pyrexia complicated by rigors, severe chills, etc., which cannot be controlled with non-steroidal anti-pyretic medication, oral corticosteroids should be started at the second event and doses should be gradually increased for subsequent events.

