8.2.6 Renal Insufficiency

Cases of renal insufficiency have occurred in subjects receiving dabrafenib and the combination of dabrafenib and trametinib. Prior to start of study treatment, concomitant medications should be reviewed for the potential risk of inducing nephrotoxicity and concomitant medications should be modified if clinically possible.

Guidelines regarding management and dose reduction for renal insufficiency considered to be related to study treatment by the investigator are provided in Table 24.

Table 24 Management and Dose Modification Guidelines for Renal Insufficiency

Serum Creatinine Level	Adverse Event Management	Action and Dose Modification
Serum creatinine increase >0.2 mg/dL (18 umol/L) but ≤0.5 mg/dL	
 • Recheck serum creatinine within 1 week • Serum creatinine increase >1 week: contact the Medical Lead. If elevation 	
 • Continue study treatment at the same dose level

(44 umol/L) above baseline	
persists beyond 4 weeks, recommend evaluation (consider renal biopsy) for etiology; consider nephrology consultation.
 
 • If pyrexia is present, treat pyrexia as per guidelines¹ 	

Serum creatinine increase >0.5 mg/dL (44 umol/L) above baseline or serum creatinine >2 mg/dL (>177 umol/L)
	
 • Monitor serum creatinine ≥ 2 times per week • Hospitalization may be necessary if serum creatinine cannot be monitored frequently • If pyrexia is present, treat pyrexia per guidelines¹ • Consult nephrologist if clinically indicated • Perform renal biopsy if clinically indicated, for example: 
 • Renal insufficiency persists despite volume repletion • Subject has new rash or signs of hypersensitivity (such as elevated eosinophil count) 	
 • Interrupt study treatment until serum creatinine recovers to baseline • Restart with study treatment²

Abbreviations: NSAIDs, non-steroidal anti-inflammatory drugs

1. NSAIDs can induce renal insufficiency, especially in subjects with dehydration; encourage oral fluids or consider intravenous fluids as clinically indicated. See guidelines for pyrexia in Section 8.2.3.

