2. Investigator may restart at either the same or a reduced dose level. Escalation of study treatment to previous dose level is allowed if another episode of renal insufficiency does not occur after 4 weeks of dose reduction. Consultation with the Medical Lead is required before restarting study treatment if there is evidence of thrombotic microangiopathy.

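### Table 21 gives two different dabrafenib rules for third and later fevers, and Tables 21 and 24 are not reconciled for fever with renal insufficiency, so sites can handle the same event differently

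*Protocol*

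**What the plan says.** Table 21 in protocol Section 8.2.3 sets the dose rules for pyrexia considered related to dabrafenib. At a first event the instruction is "Interrupt treatment with dabrafenib; continue treatment with trametinib". The next step is "Once pyrexia resolves to baseline, restart treatment with dabrafenib at the same dose level", and the one after it is "If fever is associated with dehydration, hypotension, or renal insufficiency, reduce dabrafenib by one dose level", with trametinib kept at its current level. A second event follows the same rules. From the third event on, the restart step is "restart treatment with dabrafenib at dose reduced by one dose level", with no condition attached. Footnote 6 is marked on that step and says "Dabrafenib should be reduced by one dose level at discretion of the investigator if pyrexia is accompanied by severe recurring rigors". It adds that the rigors must be beyond best supportive care, and it allows re-escalation after four weeks without fever.

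Table 24 in Section 8.2.6 covers renal insufficiency that the investigator considers related to study treatment. For a creatinine rise above 0.2 and up to 0.5 mg/dL over baseline, study treatment continues at the same level. For a rise above 0.5 mg/dL, or a value above 2 mg/dL, the action is "Interrupt study treatment until serum creatinine recovers to baseline". The restart footnote is "Investigator may restart at either the same or a reduced dose level". In both rows the management column refers the site to the pyrexia guidelines if fever is present.

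Section 6 allows the term study treatment to mean either drug or the combination. Section 1.4 agrees with Table 21 that trametinib stays at the same dose during fever.

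**The concern.** Fever together with renal insufficiency is an overlap that the protocol itself expects. Section 1.4 warns that complicated pyrexia can lead to acute renal insufficiency. Section 11.2(h) makes that combination a protocol-specific serious adverse event when there is no obvious infectious cause. SAP Section 2.7.1.1 lists both pyrexia and renal failure as events of special interest. A site facing such an event has two specific dosing tables open and needs them to agree, or to say which one leads. A site managing a third fever needs the row and its footnote to say the same thing.

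Patient safety comes first: the instructions concern when a drug is held and the dose at which it restarts. The exposure data are also affected. SAP Section 2.3.3 counts dose reductions and interruptions by number and reason for each drug and computes compliance against the full daily dose (300 mg for dabrafenib). SAP Section 2.7.1 tabulates adverse events leading to interruption or reduction. If sites read the tables differently, those counts mix tolerability with interpretation. Amendment 11 records 55 subjects still on treatment at 6 April 2020, so the instructions were still in use.

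**Working it through.** The plan gives no figure to reproduce, so the check is a comparison of text plus one short dose calculation.

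**A. Table 21, third and later fevers**

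| Source | Is reduction required? | Condition |
|---|---|---|
| Subsequent Events row, step 2 | Yes, one level | None |
| Footnote 6, marked on that step | Investigator's discretion | Severe recurring rigors not managed by best supportive care |

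The two lead to the same action only in subjects who have such rigors and whose investigator chooses to reduce. For a third fever without them, the row reduces and the footnote gives no ground to reduce.

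The placement of the footnote markers does not explain this. In the First Event row, marker 7 (a corticosteroid note) sits on a dose step. In the Second Event row, marker 6 (a dose note) sits on a corticosteroid step. Those two look interchanged. In the Subsequent Events row, each marker matches the content of its step.

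How far apart can the readings go? Table 9 gives dabrafenib levels of 150, 100 and 75 mg BID. Section 8.1 stops dabrafenib if less than 75 mg BID would be needed. Assume five fevers, no reduction at the first two, and no severe rigors:

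- Row, never re-escalated: 3rd event 100 mg; 4th event 75 mg; 5th event below the floor, dabrafenib stopped.
- Row, re-escalated to 150 mg after each reduction (four fever-free weeks each time): 100 mg at each of the 3rd, 4th and 5th events.
- Footnote 6 alone: 150 mg throughout.

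**B. Fever with renal insufficiency, both considered treatment-related**

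| Item | Table 21 | Table 24, rise >0.5 mg/dL | Table 24, rise >0.2 to ≤0.5 mg/dL |
|---|---|---|---|
| Dabrafenib during the event | Interrupt | Interrupt, if included in study treatment | Continue, same dose |
| Restart trigger | Fever resolved (the only one stated) | Creatinine back to baseline | None needed |
| Dabrafenib dose afterwards | One level lower | Same or lower | Same |
| Trametinib | Continue | Interrupt, if included in study treatment | Continue |

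For the larger rise:

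- The triggers diverge whenever fever settles before creatinine does.
- The trametinib instructions diverge if study treatment means both drugs.
- The doses do not exclude each other. A one-level reduction satisfies both tables, so the difference is mandatory versus optional.

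For the smaller rise, Table 24 continues treatment while Table 21 interrupts dabrafenib. Table 21 also reduces it if such a rise counts as renal insufficiency, for which it gives no creatinine threshold.

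**C. Is there a rule of precedence?**

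- Table 24 points to the pyrexia guidelines, but only in its management column; its own dose column still stands.
- Section 1.4 points to Section 8.2.6 for renal failure, including the management of pyrexia, but does not rank the tables.
- Section 8.1 asks investigators to use clinical judgment, in text that introduces the general guidelines for events without specific ones. It does not rank two specific tables.

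None of these says which table governs dose and restart.

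**The case against.** The strongest reply is that the tables can be layered: the fever follows 8.2.3, the creatinine follows 8.2.6, and the cross-references point that way. On that reading, continuing trametinib in a pyrexia table need not cancel a hold for a different toxicity. Further, the fever-resolution trigger sits in the step that restarts at the same dose. The renal insufficiency step gives no trigger of its own, so Table 24's could fill the gap. Each table also applies only if the investigator attributes the event to treatment, and Section 1.4 allows that renal insufficiency with fever may be secondary to dehydration or hypotension. Footnote 6 could be read as an extra option plus a re-escalation rule rather than a limit on the row.

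All of these are possible readings, and they narrow the point. None of them is written down, and a site that adopts the other reading in each case is also following the text.

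A reader might infer more than the documents support:

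- That no site can comply with both tables on restart dose. This fails, because Table 24 accepts a reduced dose.
- That sites will diverge. The text shows only that they can, and Section 8.1 leaves room for judgment.
- That about a third of febrile subjects here are affected, or would lose dabrafenib at a fifth fever. The one-third figure is earlier combination experience. It overstates the conflict to the extent that row and footnote lead to the same action, and it says nothing about fever with renal insufficiency. The step-down ignores re-escalation, which is permitted.

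**Conclusion.** The point holds in a limited form. Table 21 contradicts itself for third and later fevers: a mandatory reduction in the row against a discretionary, rigors-linked one in the footnote. This is the firmest part. Separately, Tables 21 and 24 are not reconciled when treatment-related fever and renal insufficiency coincide. The gaps there are the restart trigger and the handling of trametinib after a creatinine rise above 0.5 mg/dL, and the handling of dabrafenib after the smaller rise. The trigger gap assumes that fever resolution also governs restart after a reduction for renal insufficiency. The trametinib gap assumes that study treatment means both drugs.

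The size in this trial is unknown: the documents give no count of subjects with fever and renal insufficiency, or with three or more fevers. The dose calculation shows only the range between readings, from no reduction to stopping dabrafenib at the fifth event, and its far end requires no re-escalation.

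A reader might also infer bias in the primary result. The documents do not support that: the study has one arm, and reductions and interruptions are summarised descriptively. The consequences are for the safety instructions and for how those summaries are read.

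**What to change.** The sponsor's medical team should decide the content; no view is given here on which dose or rule is right. Three wording changes are needed:

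1. Make the Subsequent Events row of Table 21 and footnote 6 state the same rule, and check the placement of markers 6 and 7 throughout the table.
2. For fever with renal insufficiency, state which table governs the restart trigger, the restart dose, and the handling of dabrafenib and of trametinib, each by name rather than as study treatment.
3. State what creatinine change counts as renal insufficiency in Table 21, so that the smaller rise in Table 24 is covered.

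The cost is wording in two protocol tables, issued with the next amendment or a letter to sites, with no new procedures or data collection. If the clarification comes late in the study, the report should note that earlier reductions and interruptions for these events were recorded under unreconciled instructions.
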